## Study plan

**Intervention.** Participants in the Group A will experience the orthotic intervention followed by the orthosis plus OT task-oriented approach intervention. Participants in the Group B will first undergo a period of no treatment followed by the OT task-oriented approach only (Figure 3).

[figure not shown]

Figure 3. Flowchart for the proposed protocol.

**Use of the Nike + FuelBand as monitor and placebo.** The Nike+ FuelBand will serve as a monitor for all participants throughout their study period. The FuelBand is a commercially available wristband designed to measure activities throughout a day. The

Orthosis for stroke  
Protocol Number: 1309M42881

wristband is available in three sizes. Researcher will adjust the length for each participant, by removing 8mm link or adding up to 16mm to each wristband.

All participants will wear the Nike+ FuelBand at the wrist level throughout the study period and will be informed that the wristband is used to monitor their use of the arms during a day. Participants experiencing the orthotic intervention (Group A) will wear the forearm rotation orthosis on top of this wristband. All participants will receive weekly phone calls from the investigator reminding them to recharge the wristband because the wristband needs to be recharged by connecting to a computer or any device with USB port every 4-7 days.

Conditions involving OT task-oriented approach intervention consists of 18 hours of intervention time (three one-hour or two 1.5-hour session per week) of functional and motor training. Each session will concentrate on how to engage the affected arm actively, effectively, and efficiently in functional tasks that are meaningful to the participant. Suggested evaluation and intervention procedures for the OT task-oriented approach are illustrated in Figure 4 and 5.

[figure not shown]

Figure 4. Flowchart for suggested evaluation procedure for OT task-oriented approach.

Copied from Almhawi (2011) with permission.

[figure not shown]

Figure 5. Flowchart for suggest treatment for OT task-oriented approach. Copied from Almhawi (2011) with permission.

The forearm rotation orthosis (Figure 6) is consisted of a commercial fabric wrist orthosis and a Latex-free neoprene strap. This orthosis is designed to assist forearm rotation without limiting functional elbow flexion and extension. During the phase of orthotic intervention only, participants will be asked to wear the orthosis on top of the Nike+ FuelBand of their affected arm during functional tasks within their context. The primary investigator will make three bi-weekly phone calls during the experiment phase for enhancing adherence with orthosis and reminding them to recharge the wristband. Participants will also be asked to wear the orthosis and the wristband for the following experiment phase, including research visits, and will be encouraged to continue wear it within their context. However, they will be asked not to wear the orthosis at evaluation sessions to maintain the integrity of the design.

Figure 6. The forearm rotation orthosis.

**Potential risk of the orthosis.** No risks regarding using the neoprene for a dynamic orthosis were identified in the literature. Using the forearm rotation orthosis for the

proposed study, we hypothesize that possible risks may include but not be limited: 1) skin irritation over contact areas, 2) increased muscle soreness when increased use of the arm, and/or 3) movement restriction of the involved upper extremity during functional tasks. Participants will need to remove the orthosis immediately and report to the primary investigator if any of above symptoms develops. Information regarding possible risks of use of the orthosis is included in the consent form as well as the written instructions (Appendix A). The primary investigator will provide verbal education and written instructions regarding orthosis use and care to the participants after orthosis fabrication.

**Data collection plan and schedule.** The timing of screening, randomization, and follow-up visits are illustrated in Figure 2. The primary investigator will screen potential participants' eligibility using the Mini-Mental Status Examination (MMSE), the Short Form Fugl-Meyer (S-FM), and ROM. There will be three time points for data collection (pretest, posttest 1, and posttest 2). Trained occupational therapy students recruited from the University of Minnesota and University of Puget Sound will serve as the blinded evaluators to implement all assessments except the COPM for each research site. The primary investigator will administer the COPM to obtain information that will be used to guide future interventions.

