## Methodology

### Study design

This study will employ a randomized, single-blinded, two-group, repeated measure design (Table 1).

Table 1. *Experimental design of the internal pilot study*

Group/Week			Week 1	Week 2-7	Week 8	Week 9-14	Week 15
M	R	A	O1	Orthosis	O2	Orthosis+OTTO	O3
M	R	B	O1	No treatment	O2	OTTO	O3

*Note.* M = matching with severity of motor function of the upper extremity; R = random assignment; O1,2,3 = time points for outcomes measures; Orthosis = six weeks of forearm rotation-assist orthotic intervention; OTTO = six weeks of OT task-oriented approach intervention.

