### Study endpoints

The primary endpoint is the functional improvement. “Functional improvement” represents improvement in the performance of everyday activities. The secondary endpoints are active range of motion and muscle strength, including grip and pinch, of the involved upper extremity as well as orthosis compliance.

Outcome measures for the primary endpoint include the *Canadian Occupational Performance Measure* (COPM) for self-perceived functional performance and satisfaction with performance, the *Wolf Motor Function Test* (WMFT) for quantitatively measuring the motor function of the upper extremity, and the *Motor Activity Log* (MAL) for measuring participants’ actual use of the involved arm in the real world.

Outcome measures used for the secondary endpoints include goniometric measurements for active and passive range of motion (ROM), hand-held dynamometry and manual muscle testing for muscle strength of the upper extremity, Jamar Dynamometer for grip strength, pinch gauge for pinch strength, as well as information collected by the Nike+ FuelBand regarding numbers of hours they wear the orthosis everyday throughout the study period for adherence with the orthosis.

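### The only stated route for capturing the named orthosis risks is self-report by wearers; no symptom question is specified for either group, so harms may be under-recorded and unequally ascertained

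*Combined protocol and SAP*

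**What the plan says.** **Risks and reporting.** Under Study plan, Potential risk of the orthosis, the protocol lists "1) skin irritation over contact areas, 2) increased muscle soreness when increased use of the arm, and/or 3) movement restriction" of the involved arm during functional tasks. The action that follows is: "Participants will need to remove the orthosis immediately and report to the primary investigator if any of above symptoms develops". Appendix A repeats this as an instruction to stop using the splint and contact the researcher. Both texts address orthosis wearers only.

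**Calls.** Two sets are described in Study plan. The FuelBand paragraph says: "All participants will receive weekly phone calls from the investigator reminding them to recharge the wristband". The orthosis paragraph describes "three bi-weekly phone calls during the experiment phase for enhancing adherence with orthosis and reminding them to recharge the wristband". Neither description mentions symptoms.

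**Visits.** Table 1 in Study design puts assessments at weeks 1, 8 and 15 and defines the first active phase: "Orthosis = six weeks of forearm rotation-assist orthotic intervention". The orthosis is taken off for evaluations.

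**Group B.** It is untreated in weeks 2-7 and has the task-oriented therapy in weeks 9-14. On the wristband: "All participants will wear the Nike+ FuelBand at the wrist level throughout the study period".

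**Outcomes and analysis.** Study endpoints states: "The secondary endpoints are active range of motion and muscle strength, including grip and pinch, of the involved upper extremity as well as orthosis compliance". Data analysis plans descriptive statistics for demographics, baseline data and adherence. No harms outcome or summary appears in either section.

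**General safety text.** Data analysis would end the study for serious adverse effects. Data monitor has the academic advisor work with the investigators on safety.

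**The concern.** A pilot of a new device should show whether people can tolerate it. Spontaneous reporting tends to miss minor problems, and here the route is set out for one group only. Two consequences pull in opposite directions.

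- Within Group A, a participant who does not volunteer a problem may leave no record of it, so the device looks better tolerated than it is. The weak period is weeks 2-7, when the orthosis is worn at home with no scheduled visit.
- Between groups, soreness from greater arm use and irritation under the wristband can arise in both, but only Group A is told to report. A comparison could make the orthosis look worse for reasons unrelated to the device.

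The plan as written gives no means of separating the two. Sample size estimation says the pilot is meant to inform a future study, and tolerability is part of what that study would need.

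**Working it through.** The plan gives no harms rate or target, so there is no figure to reproduce. The check is to list each scheduled contact, see what the text says it is for, and then gauge scale.

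**Step 1. Contacts and their stated purpose**

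| Contact | Who | Stated purpose | Symptom question specified? |
|---|---|---|---|
| Weekly calls | Both groups | Recharge reminder | No |
| Three bi-weekly calls, orthosis-only phase | Group A | Adherence and recharge reminder | No |
| Weeks 8 and 15 (O2, O3) | Both groups | COPM, WMFT, MAL, range of motion, strength | No |
| Therapy sessions, weeks 9-14 | Both groups | Functional and motor training | No |
| Self-initiated report | Orthosis wearers | Named risks; Appendix A list | Not asked; volunteered |

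**Step 2. The gap.** O1 is in week 1 and O2 in week 8. Weeks 2 to 7 are 7 - 2 + 1 = 6 weeks with calls but no scheduled visit.

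**Step 3. Shared exposure.** Both groups wear the wristband throughout. In weeks 9-14 both have the same therapy: three 1-hour or two 1.5-hour sessions a week, so 3 x 6 = 18 hours. Band irritation and use-related soreness are possible in both groups. Irritation under the orthosis itself has no exact Group B counterpart.

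**Step 4. Consistency of the reporting list.** The risk paragraph says risk information is in Appendix A. The stop-and-contact list there gives swelling, allergic or other skin problems, discomfort and an open wound. Muscle soreness and movement restriction are not named, although discomfort might be read to cover some of it.

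**Step 5. Scale.** Treatment allocation gives 5 per group in each of three severity strata, so 3 x 5 = 15 per group and 30 in all, matching the planned enrolment. Let p be the true symptom rate and c the share of cases that reach the record. Both are assumptions, since the documents give neither. The chance of recording at least one case among 15 is 1 - (1 - pc)^15:

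| p | c = 1 | c = 0.5 | c = 0.25 |
|---|---|---|---|
| 5% | 0.537 | 0.316 | 0.172 |
| 10% | 0.794 | 0.537 | 0.316 |
| 20% | 0.965 | 0.794 | 0.537 |

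**Step 6. What a clean record would show.** With every case captured, 0 of 15 gives an upper limit of 1 - 0.05^(1/15) = 0.181 (one-sided 95%) or 1 - 0.025^(1/15) = 0.218 (upper end of the two-sided 95% interval). Under spontaneous reporting, even these limits cannot be claimed.

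**The case against.** The strongest reply is that the plan has more safety content than its list of endpoints suggests.

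- The advisor monitors safety, serious adverse effects end the study, and wearers get verbal and written instructions to stop and make contact. All of this is in the text. None of it says how symptoms are elicited, defined or recorded, so it softens the point without answering it.
- The named problems are ones a wearer would notice, participants must be able to follow three-step instructions, and the investigator to whom they report telephones repeatedly. That makes volunteering easier, but reporting still depends on the participant.
- Range of motion and strength are measured in both groups at O2 and O3, so a lasting loss is compared. The orthosis is also worn at research visits in weeks 9-14, where the therapist sees it in use. Both stand. They do not cover skin problems or soreness, nor restriction during wear in weeks 2-7, and no structured check is specified at the therapy visits.

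A reader might go further and infer that the callers never ask about symptoms, or that Group B is bound to show no events. The documents do not support either. They state what the calls are for without excluding other questions, and Group B has weekly calls and 18 hours of therapy in which a complaint could be raised. A reader might also conclude that the trial can say nothing about tolerability. That is too broad, because wear hours give partial, indirect information. The consent form and the figures were not available and may contain more.

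**Conclusion.** The concern holds in a limited form. In the available text, self-initiated reporting by wearers is the only specified route for capturing the three named risks. No symptom question is specified at any scheduled contact, and none is directed to Group B. Under-recording in Group A is therefore possible, most of all in weeks 2-7, and a comparison of soreness or skin problems between groups would rest on unequal ascertainment.

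The size cannot be fixed, because it depends on assumed rates. At a 10% true rate, the chance of recording any case among 15 falls from 79% with full capture to 54% if half are volunteered and 32% if a quarter are. This is a cheap improvement to data collection. It does not call into question the efficacy analysis or the comparison of lasting range or strength.

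**What to change.** Ask every participant in both groups the same fixed questions at calls that both groups already receive, and at O2 and O3 when the primary investigator gives the COPM, so that the blinded evaluators are not involved. The questions cover skin problems under the band or orthosis, muscle soreness, and restricted arm movement in daily tasks. Record yes or no, the date, and whether the device was removed. Report counts by group and phase descriptively.

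Two places need reconciling at the same time:

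- The call schedule is weekly in the FuelBand paragraph and three bi-weekly calls in the orthosis paragraph. Both include the recharge reminder, and the text does not say whether they are the same calls.
- The symptom list in Appendix A differs from the risks named in the protocol body.

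The remove-and-report instruction stays as the sponsor sets it.

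The cost is a three-question checklist of about two minutes per contact and one table. Three limits should be stated. Direct questions will raise the count of minor symptoms in both groups. The primary investigator assigns the groups and so is unblinded, which leaves some ascertainment bias. With 15 per group, 0 of 15 would still allow a true rate of about 18% (one-sided) to 22% (two-sided).

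### Appendix A's stop-and-contact list omits movement restriction, which the protocol makes a reason to remove the orthosis and report

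*Combined protocol and SAP*

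**What the plan says.** Under Study plan, the paragraph on potential risk of the orthosis lists three hypothesised risks: skin irritation where the device touches the arm, more muscle soreness with greater arm use, and "movement restriction of the involved upper extremity during functional tasks". It then gives participants a duty to act: "Participants will need to remove the orthosis immediately and report to the primary investigator if any of above symptoms develops". The next sentence says where they are told: "Information regarding possible risks of use of the orthosis is included in the consent form as well as the written instructions (Appendix A". The paragraph ends with a further channel: "The primary investigator will provide verbal education and written instructions regarding orthosis use and care to the participants after orthosis fabrication".

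Appendix A is the instruction sheet. Its section on when to stop using the splint has four entries: swelling of the arm, an allergic or other skin reaction, finding the splint uncomfortable, and an open wound beneath it. A closing sentence asks the participant to contact the researcher about any of these.

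**The concern.** The protocol relies on the participant to recognise a symptom, take the device off and report it. The sheet is the written form of that rule which the participant receives. If a trigger is in the protocol but not on the sheet, someone can follow the sheet exactly and still miss what the protocol requires.

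The setting makes this matter more. Table 1 gives Group A "six weeks of forearm rotation-assist orthotic intervention" before any therapy begins, and the device is worn in the participant's own surroundings. The planned calls have other stated purposes. One series is described as "All participants will receive weekly phone calls from the investigator reminding them to recharge the wristband", the other as "three bi-weekly phone calls during the experiment phase for enhancing adherence with orthosis and reminding them to recharge the wristband". Neither mentions asking about symptoms.

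The omitted trigger is also the one closest to the purpose of the device, which is meant to assist forearm rotation while leaving ordinary elbow movement free. An arm that moves less in the orthosis would be a sign that it is not working as designed.

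**Working it through.** The plan gives no figure to reproduce on this point. The check sets the protocol's triggers against the sheet, then counts who is exposed and what contact they have.

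**Step 1. Triggers against the stop list.** The triggers come from the potential-risk paragraph under Study plan, and the list from Appendix A.

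| Protocol trigger (remove and report) | On the Appendix A stop list? |
|---|---|
| Skin irritation | Yes, under the skin-reaction item |
| Increased muscle soreness | Not named; implicitly within the discomfort item |
| Movement restriction | No |

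Swelling and open wound are on the sheet but are not among the three protocol triggers. They are sensible additions and do not fill the gap.

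**Step 2. The rest of Appendix A.** The description of the splint, the steps for putting it on, and the care and cleaning notes were read for any mention of restricted movement. The only mention of restriction is in the steps for putting it on, where it concerns circulation under a tight strap. It is not part of the stop list.

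**Step 3. Completeness of the list.** The four items are joined as alternatives, the last ends with a full stop, and the contact sentence follows directly. Nothing suggests an item lost in text extraction.

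**Step 4. Size of the gap.** Triggers neither named nor implicitly covered: 3 − 1 (skin) − 1 (soreness) = 1 of 3. The discomfort item would also catch restriction that is uncomfortable, so what remains is restriction without discomfort.

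**Step 5. Who is exposed, and with what contact.**

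- Group A (Treatment allocation): 3 severity groups × 5 = 15 of the 30 planned participants.
- Orthosis-only phase (Table 1): weeks 2 to 7, which is 7 − 2 + 1 = 6 weeks, with 0 therapy sessions.
- Calls in that phase: 6 weeks × 1 weekly call = 6. If the three bi-weekly calls are separate, 6 + 3 = 9.
- Weeks 9 to 14: wear at home continues, since participants "will be encouraged to continue wear it within their context", but a therapist sees them regularly. Sessions are 6 × 2 = 12 (1.5 hours each) or 6 × 3 = 18 (1 hour each). Both agree with the stated 18 hours: 12 × 1.5 = 18 and 18 × 1 = 18.

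The gap therefore matters most in weeks 2 to 7 and less afterwards. The documents give no event rate for any of the three risks, so no expected number of affected participants can be calculated.

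**The case against.** The case for leaving this alone has four parts.

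*Other channels may carry the message.* The protocol says the risks are in the consent form as well as the sheet, and the investigator gives verbal education. The academic advisor also has a safety-monitoring role (Data monitor). The consent form could not be examined, so nothing can be called missing from it. This stands as a limit on the consequence: it cannot be said that participants are never told. It does not remove the mismatch, because the protocol says that the risk information is in both documents, and for this risk that is not true of Appendix A.

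*The remaining gap is narrow.* Discomfort is a broad, subjective item that will catch some restriction. The three risks are hypothesised, and the documents describe no harm from painless restriction. This also stands and keeps the point at low priority. But the protocol's rule does not depend on discomfort, so the sheet is narrower than the rule it is meant to convey.

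*A new line could misfire.* The device includes a wrist orthosis. It is a reasonable inference, though not stated in the documents, that some limitation at the wrist is normal. An unqualified instruction might lead participants to stop for ordinary device behaviour, and adherence is a secondary endpoint. This is really an objection to the protocol's own trigger, which is equally unqualified. It does support more careful wording.

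*The counts say little.* One of three is a count of list items, and 15 is simply the size of Group A; neither measures risk. That is correct, and they are not offered as such. It was also argued that only three calls might apply to Group A. The protocol promises weekly calls to all participants, so six is the lower bound.

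**Conclusion.** The concern holds. The protocol makes movement restriction a trigger for immediate removal and report, and Appendix A, cited as carrying the risk information, does not mention it. One of three triggers is missing from the sheet, and in practice the omission matters when restriction occurs without discomfort.

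Confidence in the textual omission is high. The safety consequence is less certain: it assumes that at least some participants rely on the sheet, and it depends on what the unseen consent form and the verbal instruction convey. This is a minor participant-safety point that is worth correcting. It does not touch the endpoints, error rates, sample size, analysis or the rule for terminating the study.

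**What to change.** Add an item to the Appendix A stop list saying that the splint restricts movement of the arm during tasks. Wording it as new or increased restriction that interferes with tasks would reduce needless stopping; if that qualifier is used, put it in the potential-risk paragraph too so that the two texts agree. For clarity only, also add increased muscle soreness in the weaker arm. Keep the four existing items, and check that the consent form lists the same triggers.

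Optionally, have the caller ask about these symptoms during the calls already planned in weeks 2 to 7.

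The cost is assumed, since the documents do not give one: a revised handout and whatever notification the review board requires. Design, sample size and analysis stay as they are.

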### **Treatment allocation**

Participants who are eligible and willing to participate in this study will first be matched with the severity of the motor function of the involved upper extremity measured by the upper extremity subscale of the Short Form Fugl-Meyer Motor Function Assessment. Participants will be classified as mild, moderate, and severe groups. Participants in each group will then be randomized in a 1:1 allocation ratio to either the Group A or B (Figure 1). The primary investigator, [name], will randomly assign eligible participants at the screening session using sealed envelopes with an equal number of both intervention

conditions to balance group size (10 for each matched group with 5 Group As and 5 Group Bs).

[figure not shown]

Figure 1. Study schematic for treatment allocation.

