### **Sample size estimation**

We plan to enroll 30 participants in the study. Based on anticipated number of screen failures and/or withdrawals, the maximum number of participants whom we will consent in order to achieve the scientific objectives of this study is 40. Note that the number of participants described above is a rough estimate of the sample size needed, since there is no evidence to address the primary question of interest. This proposed project involves pilot/preliminary investigation, which will be used to calculate the effect sizes that need to be used for the future study.

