### **Data monitor**

The academic advisor, [name], is the founder of the OT task-oriented approach. He will monitor study procedures to ensure fidelity to the OT task-oriented approach. The academic advisor will work closely with the study investigators for safety monitoring throughout the study period. He will supervise the primary investigator, [name], with the development and implementation of the treatment plan for study participants. The principle investigator will train the blinded evaluators of both sites on all assessment tools until total agreement is achieved. The blinded assessor will execute all evaluations and the primary investigator will complete the data entry accumulatively. The

Orthosis for stroke  
Protocol Number: 1309M42881

academic advisor will also check and monitor the accuracy of data collection, data entry, and data analyses.

All information gathered for the study will be converted into digital files and uploaded within 24 hours to the “Box” secure storage operated by the University of Minnesota. The Box is an online storage space that allows storing Protected Health Information (PHI). Only the principle investigator has the access to “Box” as it requires duo-factor authentication to log in. Information on the “Box” is at <http://box.umn.edu>

Subjects’ name and contact information will be kept in a separate file from the data gathered from the study using an ID code. All printed documents will be converted into digital files and uploaded to Box. Printed documents will then be immediately shredded.

Identifying materials such as the consent forms gathered from the University of Minnesota site will be kept in a locked file cabinet in the rehabilitation science graduate student office, which requires security code for access. Personnel from the department have access to the office. However, only the primary investigator has access to locked file cabinet that keeps the study information. Identifying materials such as the consent forms obtained from the onsite clinic at the University of Puget Sound will be kept in a locked file in the Occupational Therapy Department at the University of Puget Sound, WEY 106. Data collected from this study will be maintained for three years after completion of the study, then shredded.

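### The COPM, one of three primary measures, is collected by an investigator who knows the group, and the document disagrees with itself on who collects it

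*Combined protocol and SAP*

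**What the plan says.** **Role of the COPM.** Study endpoints lists the COPM, the Wolf Motor Function Test (WMFT) and the Motor Activity Log (MAL) as the measures of the primary endpoint. The COPM gives the participant's own view of performance and of satisfaction with it.

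**Who collects what.** Under Study plan (data collection plan and schedule), trained students act as blinded evaluators "to implement all assessments except the COPM for each research site". The next sentence reads: "The primary investigator will administer the COPM to obtain information that will be used to guide future interventions". Treatment Fidelity (Blinded evaluator) repeats the exception. Neither place limits it to the pretest, so as written it covers O1, O2 and O3.

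**What that investigator knows.** Under Treatment allocation, the primary investigator "will randomly assign eligible participants at the screening session using sealed envelopes". Under Study plan (Intervention), he also gives the orthosis education and makes three bi-weekly adherence calls.

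**The conflicting statement.** Data monitor says: "The blinded assessor will execute all evaluations and the primary investigator will complete the data entry accumulatively". It makes no exception for the COPM. The same section says that the principal investigator "will train the blinded evaluators of both sites on all assessment tools", whereas the training list in Treatment Fidelity names the WMFT, MAL, range of motion and strength and omits the COPM.

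**The concern.** A rating given in an interview can be influenced by the interviewer, and here the interviewer knows the group. The plan protects evaluator blinding elsewhere, for example by keeping the orthosis off at evaluation sessions, but leaves one primary measure outside that protection.

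The exposure is clearest at O2. By then Group A has had the orthosis and the education and adherence calls from the interviewer himself. Group B has had no treatment and only the recharge calls that everyone receives. O2 is the one comparison of orthosis with no treatment, and functional performance is part of hypothesis 1.

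The baseline rating may be affected too. Table 1 puts allocation before the first measurement ("R = random assignment; O1,2,3 = time points for outcomes measures") and allocation takes place at screening. Whether the O1 COPM follows allocation cannot be confirmed, because Figure 2 is not shown.

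The pilot also has a downstream use. Sample size estimation describes it as an investigation "which will be used to calculate the effect sizes that need to be used for the future study". If the COPM is used for that purpose, a biased difference could enter the planning of the next study.

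**Working it through.** **Step 1. The text side by side.**

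| Section | Who does the COPM |
|---|---|
| Study plan, data collection | Primary investigator; evaluators do the rest |
| Treatment Fidelity, Blinded evaluator | Not the evaluators |
| Data monitor | Blinded assessor does all evaluations |

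The third row contradicts the first two. The investigator's knowledge of the group follows from Treatment allocation and Study plan alone. That he is also the principal investigator who treats most participants (Treatment Fidelity) is likely, because the advisor supervises both roles on the treatment plan. It remains an inference, since names are removed, and the point does not need it.

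**Step 2. Does the stated reason require this arrangement?** Guiding treatment requires the investigator to have the problem list and see the ratings. It does not require him to collect the scores, least of all at O3, after which Table 1 shows no treatment.

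**Step 3. Illustration at O2.** The documents give no estimate of bias, no significance level and no correlation, so there is no figure of the plan's to reproduce. From the documents: three severity groups of 10, so 3 × 5 = 15 per group; O2 analysed with the pretest as covariate (Data analysis). Assumed: two-sided 0.05, correlation r = 0.6 between visits, no true effect, and a differential shift s, in SD units, of which a fraction f is already present at O1.

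- Standard error = √[(2/15)(1 − 0.6²)] = √(0.1333 × 0.64) = 0.292 SD
- 95% CI half-width = t(0.975, 27 df) × 0.292 = 2.052 × 0.292 = 0.60 SD
- Bias of the adjusted difference = s(1 − r·f)
- False-positive rate from the noncentral t with 27 df and noncentrality bias/0.292

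| Share of shift at O1 | s = 0.2 | s = 0.3 | s = 0.5 |
|---|---|---|---|
| None (f = 0) | bias 0.20; 10% | 0.30; 17% | 0.50; 38% |
| Half (f = 0.5) | 0.14; 8% | 0.21; 11% | 0.35; 21% |
| All (f = 1) | 0.08; 6% | 0.12; 7% | 0.20; 10% |

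Other correlations, for s = 0.2/0.3/0.5: with r = 0.4, 9/14/30% for f = 0 and 6/8/14% for f = 1; with r = 0.8, 14/26/60% and 5/6/7%.

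**Step 4. O3.** Data analysis adjusts O3 for posttest 1. With shifts s2 at O2 and s3 at O3, the bias is s3 − 0.6·s2.

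- Shift gone by O3 (s3 = 0): −0.6 × 0.2/0.3/0.5 = −0.12/−0.18/−0.30 SD, against the orthosis.
- Shift unchanged (s3 = s2): 0.4 × 0.2/0.3/0.5 = +0.08/+0.12/+0.20 SD, in its favour.

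The sign is therefore undetermined. The same holds for the within-group change from O2 to O3, whose bias is the shift in that group at O3 minus its shift at O2: a score already raised at O2 makes the change look smaller, and a score raised only at O3 makes it look larger.

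**Step 5. The future study, if the COPM is used to size it.** Two-sample t test, two-sided 0.05, 80% power, assumed true effect 0.50 SD: 64 per group. An estimate too high by 0.08 (0.58) would plan 48, with true power 68%. One too high by 0.20 (0.70) would plan 34, with true power 53%.

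**The case against.** **The exception is deliberate and disclosed.** It is stated twice with a reason, the design claims only single blinding, and the remaining assessments stay blinded. The Data monitor sentence may be loose wording beside two specific statements. This stands as mitigation. The conflict still needs correcting, and the reason covers treatment planning but not outcome scoring.

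**The gain is partial.** The COPM is self-rated, and participants know whether they wear an orthosis. A blinded interviewer would not remove their expectations, nor any wish to please a therapist who later sees the ratings. This stands: only the interviewer's contribution is avoidable, and how large that is is unknown.

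**The figures are all assumed.** This also stands. At the smaller shifts the bias is modest beside a confidence half-width of 0.60 SD.

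**Stronger readings that a reader might infer.** Four go beyond the documents:

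- *That the investigator biases O2 because he treats most participants.* Task-oriented therapy runs in weeks 9 to 14, after O2, and then in both groups. What matters at O2 is knowledge of the allocation, the education and the adherence calls.
- *That the COPM result is inflated in favour of the orthosis throughout.* Step 4 shows that the direction at O3 is open.
- *That biased effect sizes will pass into the next study.* Sample size estimation does not say that the COPM will be the measure used, and the other two primary measures are collected by blinded evaluators.
- *That the trial's blinding fails as a whole.* The exception concerns the COPM alone. The investigator's screening tests serve eligibility.

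**Conclusion.** The point holds in a limited form. One of three primary measures is collected by someone who knows the group, and the document contradicts itself on who collects it. The contradiction is a matter of text and needs no assumption. The bias is a risk, located mainly in the O2 comparison of orthosis with no treatment; at O3 its direction is undetermined. Its size cannot be derived from the documents. The figures in the working show only what assumed shifts of 0.2 to 0.5 SD would do with 15 per group. A change is worth making because the avoidable part of the bias can be removed cheaply, not because a large bias has been shown.

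**What to change.** 1. Have each site's existing blinded evaluator collect the COPM performance and satisfaction ratings at O1, O2 and O3, as the last item of the visit and from a fixed script. Ask participants not to mention their group or the orthosis.
2. Let the investigator still draw up the problem list and receive the ratings for treatment planning.
3. Make Study plan (data collection), Data monitor and Treatment Fidelity agree on who collects the COPM, and add it to the evaluator training list in Treatment Fidelity.

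**Cost.** No new staff and no extra visit; some training and a little time at each visit. The main drawback is carry-over. Each evaluator follows the same participants, so one who learns the group during the O2 COPM could be influenced in the O3 WMFT and MAL. Putting the COPM last protects only the current visit. As an illustration, if a quarter of participants revealed their group and the same assumed shifts applied to measures unbiased at O2, the O3 bias would be 0.25 × 0.2/0.3/0.5 = 0.05/0.08/0.13 SD, with false-positive rates of 5/6/7%. Expectation bias among participants remains.

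**Alternative.** If the sponsor keeps the present arrangement, correct the Data monitor sentence and report the COPM as an unblinded measure.
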